10.2 LIST OF ANTICIPATED POTENTIAL ADVERSE EVENTS

Anticipated potential adverse events include those that might reasonably be expected to occur in this study because they are associated with dry eye disease, the risk analysis for TearCare System (albeit remote likelihood), study testing methods or potential risks associated with warm compresses and lid massage.

- Burn, erythema, or swelling of the eyelids
- Conjunctival injection (Moderate or severe)
- Conjunctival abrasion
- Corneal abrasion
- Corneal deformation
- Allergic or inflammatory reaction to medical adhesive on the iLid device

- Formation of a chalazion or stye
- Loss in BCVA of 2 lines or greater
- Worsening of dry eye symptom
- Increased discomfort or pain of ocular surface (grittiness, foreign body sensation, etc.)
- Discomfort or pain of eyelids or orbit

10.3 REPORTING ADVERSE EVENTS AND UNANTICIPATED ADVERSE DEVICE EFFECTS

Identification, collection and reporting of adverse event information is the responsibility of the principal investigator. The investigator records the date of the event, its severity, treatment (if any) and the assessed relationship of the event to the study device on the Adverse Event Case Report Form (AE CRF).

Any ocular-related **serious adverse event** (SAE) should be reported to the study sponsor within one working day of learning of the event. Non-ocular-related SAEs should be reported to the study sponsor within two working days of learning of the event. Email the AE CRF to [contact].

Any unanticipated adverse device effects (UADE) must be reported to the following two entities:

- The study sponsor Within one working day of the investigator first learning of the event, e-mail the AE CRF to [contact]; and
- 2. The reviewing IRB As soon as possible, but no later than 10 working days after the investigator first learns of the event, report per the IRB's instructions.

The sponsor will conduct an evaluation of unanticipated adverse device effects. If the sponsor determines that an unanticipated adverse device effect presents an unreasonable risk to subjects, parts of the investigation presenting risks will be terminated. Termination will occur no later than 5 working days after the sponsor makes such a determination and no later than 15 working days after the sponsor first received notice of the effect.

11 RISK-BENEFIT ANALYSIS

11.1 ANTICIPATED CLINICAL BENEFITS

The TearCare™ procedure will be performed with the aim of reducing the signs and symptoms of dry eye. The goal of the procedure is to provide a safe, reproducible, and

effective treatment for dry eye disease, a disease for which there is an unmet need for effective therapies.

11.2 ANTICIPATED ADVERSE DEVICE EFFECTS

Anticipated adverse effects associated with the TearCare System have been described above in Section 10.2.

11.3 RESIDUAL RISKS ASSOCIATED WITH THE TEST DEVICE, AS IDENTIFIED IN THE RISK ANALYSIS REPORT

Sight Sciences believes that there are no Intolerable residual risks from this non-invasive, controlled heat treatment device that can be easily and quickly removed by the subject or by the supervising ophthalmologist, in the event of a complication during a TearCare treatment session.

11.4 RISKS ASSOCIATED WITH PARTICIPATION IN THE CLINICAL INVESTIGATION

All anticipated study risks are listed in Section 10.2.

11.5 Possible interactions with concomitant medical treatments

It is anticipated that there will be no interactions with concomitant medical treatments.

11.6 Steps that will be taken to control or mitigate the risks.

The major risks to the subjects and the steps taken to control or mitigate them are described below:

1. Overheating of the eyelids: All TearCare treatments will be done in the investigator's office under direct supervision of the investigator. The device delivers heat to the eyelids at a temperature ranging from 41-45°C. This temperature range was selected because it is both safe for eyelid heating and

effective for melting obstructions in the meibomian glands.^{48,49,50,51} The user can adjust the temperature up or down to a level that is comfortable, and may also shut off the System at any time if it is too uncomfortable or painful. In addition, the TearCare System continuously monitors and regulates the temperature at the tissue-contacting surface of the iLid devices and has been designed to not exceed the maximum allowable temperature.

- 2. Corneal abrasion: If the iLid devices are not positioned properly or come loose during the treatment, there is the potential for a corneal abrasion. To mitigate this, the supervising physician will apply the strips to the subject and will monitor their position during the treatment to ensure they remain in place and secure.
 - In addition, there is the possibility of corneal abrasion or abrasion of the eyelid surface during expression of the meibomian glands. To reduce the chance of abrasion, the forceps have been designed with smooth surfaces (i.e. no rough edges) and only trained users will perform expression.
- Worsening of dry eye symptoms: It is possible that subjects will experience a
 worsening of dry eye symptoms during the study. Subjects will undergo a
 complete eye exam at each visit and if any untoward or worsening signs of
 ocular surface disease are observed, they will be treated appropriately.

In addition to the above, the following mitigation steps have also been taken to reduce the risks in this study:

- The device has been tested to demonstrate that it meets performance and safety specifications, as described in Section 5.1.
- Instructions for Use are provided with each device.
- The clinician using the device will be trained in how to safely and correctly apply and remove the iLid devices, and operate the TearCare System.

12 STATISTICAL CONSIDERATIONS

12.1 EVALUABILITY

All subjects on whom the TearCare device is attempted will be considered evaluable for the safety analysis. All eyes that have at least one postoperative visit and have no major protocol deviations will be evaluable for the per protocol analysis.

12.2 Analysis Populations

The per-protocol analysis population includes all subjects who have at least one post-treatment visit and have no major protocol deviations, including specifically no use of dry-eye medications (Xiidra, Restasis). The primary and secondary endpoint analyses will be carried out on the per-protocol population. The primary analysis population will be per-protocol.

The intent-to-treat (ITT) analysis population includes all subjects who are randomized to either arm, regardless of treatment received. The primary and secondary endpoint analyses will also be carried out on the ITT population as well.

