treatment to naturally express melted meibum, the physician then uses the ExpressTM Forceps to further express the meibomian glands manually immediately following the eyelid heat treatment.

In this study, the TearCare System will be compared with standard-of-care warm compress treatment and lid massage in patients with dry eye disease. The objective is to demonstrate that the TearCare System is safe and effective in relieving the signs and symptoms of dry eye disease and that it is superior to a commonly prescribed, standard treatment of warm compress and lid massage.

The TearCare System is a Class II-exempt device that is currently listed and commercially available in the US. This study is being conducted to collect data to update the indication for use for the TearCare System to read as follows, "The TearCare® System is indicated for the treatment of the signs and symptoms of dry eye disease (DED).

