9.2 NUMBER OF SUBJECTS, DURATION OF FOLLOW-UP AND STUDY DURATION

A total of 200 subjects will be enrolled and randomized in the study. Assuming a 15% screen failure rate, approximately 230 subjects will be enrolled and screened to obtain 200 randomized subjects. All subjects will be followed for 12 months.

It is anticipated that enrollment in the study will take 3-6 months. Including the 12-month follow-up period, the study is expected to last 15-18 months.

Analysis of the primary outcome will occur when the last subject has reached the 1 month follow up. In order to evaluate long-term results of the TearCare treatment, data will be re-analyzed after the last subject reaches the 6 month follow-up and then again after the last subject reaches the 12 month follow up.

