9.8 Management of Dry Eye Symptoms During Follow-Up

During follow-up, if subjects require drops to relieve their dry eye symptoms, they may use Refresh® Plus lubricant vials which have been supplied by the investigator. Other types of over-the-counter lubricants should not be used. Subjects should bring the unused vials to each follow-up visit so that they can be counted.

Subjects should not use Restasis or Xiidra during the study. Use of these drugs will result in the subject being excluded from the "Per Protocol" analysis from the time of initiation of these drugs forward.

Subject should not be treated with other dry eye treatments (e.g. LipiFlow, punctal plugs, etc.) during the course of the study. Administration of these treatments will

result in the subject being excluded from the "Per Protocol" analysis from the time of initiation of these treatments forward.

NOTE: If a subject had a punctal plug at the baseline visit and it falls out during the study, it should be replaced.

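### Per-protocol is the primary population in a superiority trial, and sections 9.8 and 12.2 disagree on who belongs to it at 1 month

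*Combined protocol and SAP*

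**What the plan says.** Section 3 (Background and Justification) sets the aim of showing that TearCare is safe and effective and that "it is superior to a commonly prescribed, standard treatment of warm compress and lid massage". Section 12.2 then says "The primary analysis population will be per-protocol". To be in that set a subject needs a post-treatment visit and must "have no major protocol deviations, including specifically no use of dry-eye medications (Xiidra, Restasis". For intent-to-treat (ITT) it adds "The primary and secondary endpoint analyses will also be carried out on the ITT population as well", without saying which result decides if the two differ. Section 12.6, which holds the hypotheses, is not in the public text.

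Section 9.8 gives a different rule. A subject who starts Restasis or Xiidra leaves the per-protocol "analysis from the time of initiation of these drugs forward". It also says "Subject should not be treated with other dry eye treatments (e.g. LipiFlow, punctal plugs, etc.) during the course of the study" and applies the same from-initiation rule to those treatments. Section 12.1 words the criterion by eye rather than by subject, a minor difference.

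On timing, section 9.2 says "It is anticipated that enrollment in the study will take 3-6 months" and "Analysis of the primary outcome will occur when the last subject has reached the 1 month follow up".

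**The concern.** In a superiority trial the protection against bias comes from comparing everyone who was randomised. The per-protocol (PP) set gives some of that up. Subjects know their arm (section 7), and worsening ocular surface signs are to be treated (section 11.6). A subject who does badly is therefore a plausible candidate for an added dry-eye treatment, and so for removal. What counts as a major deviation is not defined further in the visible text.

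The choice carries far. The 1-month TBUT test gates the secondary endpoints (23.1.4) and the 3- and 6-month duration tests (12.5.6).

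The two PP rules also give different datasets. A subject who starts Restasis after a valid 1-month visit, but before the 1-month analysis, loses the 1-month value under 12.2 and keeps it under 9.8. Such use can follow from the 1-month result itself, so the 12.2 rule adds response-related exclusions that the 9.8 rule does not.

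**Working it through.** **1. The plan's own figure.** Sections 12.7 and 23.2.4 claim more than 90% power with 100 per arm. Alpha is not visible; two-sided 5% is assumed.
- TBUT (23.2.1: 6 v 4 s, SDs 3 and 2), worst case of fully correlated eyes: SE = √(9/100 + 4/100) = 0.361; 2/0.361 = 5.55; power above 99.9%.
- OSDI (23.2.2: 18.5 v 10 points, SD 18): SE = 18√(2/100) = 2.55; 8.5/2.55 = 3.34; power 91.4%.

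The claim reproduces at 100 per arm. The steps below use 90 per arm, after the planned 10% dropout.

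**2. How far the two PP rules differ at 1 month.** Assume uniform enrolment over E months (E = 3 or 6, section 9.2), analysis when the last subject reaches month 1, and a constant start rate h per month (not in the documents). Exposure that counts is 1 month under 9.8. Under 12.2 it is uniform from 1 to 1 + E months, with mean 1 + E/2 = 2.5 or 4. Expected exclusions of 180:
- 9.8: 180 × (1 − e^(−h))
- 12.2: 180 × [1 − (e^(−h) − e^(−h(1+E)))/(hE)]

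At h = 0.01 under 9.8: 180 × (1 − 0.99005) = 1.8. Under 12.2 with E = 3: 180 × [1 − (0.99005 − 0.96079)/0.03] = 4.4. With E = 6: 180 × [1 − (0.99005 − 0.93239)/0.06] = 7.0.

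| Start rate per month | 9.8 | 12.2, E = 3 | 12.2, E = 6 |
|---|---|---|---|
| 0.5% | 0.9 | 2.2 | 3.6 |
| 1% | 1.8 | 4.4 | 7.0 |
| 2% | 3.6 | 8.8 | 13.7 |

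**3. What response-related exclusion does when there is no true effect.** Assumptions: one value per subject, 90 per arm, SD 2.5 (between the planned 2 and 3), one-sided 2.5%, unequal-variance t-test, 40,000 runs. A fixed number is excluded with probability weight exp(−k × standardised outcome), k = 0.5 (weak) to 1.5 (strong).

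| Excluded, TearCare v control | Shift in difference (s) | One-sided error |
|---|---|---|
| none | 0 | 2.4-2.6% |
| 2 v 0 | +0.03 to +0.08 | 2.9-4.1% |
| 4 v 0 | +0.06 to +0.15 | 3.5-6.3% |
| 9 v 0 | +0.13 to +0.32 | 5.4-14.5% |
| 2 v 4 | −0.03 to −0.08 | 1.7-2.2% |
| 0 v 4 | −0.06 to −0.15 | 1.0-1.8% |
| 0 v 9 | −0.13 to −0.32 | 0.3-1.1% |
| 4 v 4, 9 v 9 | about 0 | 2.4-3.4% |

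Hand check for 4 v 0, weak: the shift is about 4/86 × 0.5 × 2.5 = 0.06 s. For 4 v 0, strong: SE = 2.5√(2/90) = 0.373, and 0.15/0.373 = 0.40, so the error is about P(Z > 1.96 − 0.40) = 5.9%, against 6.3% simulated.

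Two eyes per subject with baseline adjustment (assumed eye correlation 0.5 and 0.8, baseline explaining 20% of variance) gives similar results: 4 v 0, 3.4-5.8%; 9 v 0, 4.6-12.8%; 0 v 9, 0.3-1.2%.

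**4. Combining steps 2 and 3.** With strong selection and a 2% monthly start rate in TearCare only, the error is 3.4-3.7% under 9.8 and 6.1-8.1% under 12.2. With drug starts in control only it is 1.6-1.7% and 0.7-0.9%.

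**5. Detection of the planned effect.** With a true 2 s difference, the test succeeds in at least 99.5% of runs with or without the exclusions.

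**The case against.** Four points have weight.

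- ITT analyses of the same endpoints are already planned, so a reader will see any disagreement. That stands. The defect is which result governs, and the missing section 12.6 might address it. But 12.2 is explicit that PP is primary.
- One-sided exclusions are the unfavourable case. If response alone drives exclusion and the arms respond alike, losses balance and the error stays at 2.4-3.4%. That also stands, with a limit: it needs equal SDs. With the SAP's SDs of 3 and 2 (assumed eye correlation 0.5), a selection that removes about 10% from each arm, moderately to fully determined by outcome, shifts the difference by +0.09 to +0.17 s and gives 4.5-7.7% error. Unmasked subjects may also act differently by arm.
- 9 v 0 is extreme. The highest drug-start count in step 2 is 13.7 of 180, about 7 per arm if even. A drug started before the 1-month visit cannot depend on that visit's TBUT, which a masked assessor reads. If the trigger correlates only 0.3 with TBUT (assumed), 9 v 0 gives 3.1-4.4%.
- Sections 9.8 and 12.2 can be harmonised by reading 9.8 as the timing rule and 12.2 as a summary whose list is not exhaustive. This is a reasonable reading, but the text does not state it, and two analysts could build different primary datasets.

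Direction also matters. The 2017 pilot (TearCare +11.7 s, warm compress −0.3 s, section 5.2.2) suggests that more poor responders would leave control, which works against TearCare.

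**Conclusion.** The concern holds and should be fixed; it does not put the trial's ability to detect its planned effect at risk. Two parts rest on text alone: PP is primary in a superiority trial, and 9.8 and 12.2 define PP differently in a way that can change the 1-month dataset.

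The size is illustrative. A few response-related exclusions confined to TearCare would move the one-sided error from 2.5% to roughly 3-6%. The same losses in control would lower it to about 1-2%. Balanced losses with equal SDs change little. The 12.2 rule removes about 2.5 to 4 times as many subjects for drug use as the 9.8 rule. Exclusion rates, selection strength, eye correlation and the significance level are assumptions, because the visible documents do not give them.

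**What to change.** 1. In 12.2, make ITT primary for the 1-month primary and secondary tests: all randomised subjects, analysed as randomised, with observed data kept regardless of Xiidra, Restasis or other dry-eye treatment. Keep PP as supportive.
2. In 12.5.6, state that the 3- and 6-month tests use the same population.
3. Reconcile 9.8, 12.1 and 12.2 into one PP definition that says whether use after the 1-month visit removes the 1-month value. Fix the meaning of a major deviation before the 1-month database lock.
4. In 23.1.3, say that the likelihood model remains the main analysis and the planned multiple imputation the sensitivity analysis, both on the ITT set. Only the population is new here. The one-timepoint model uses no outcome from a subject without a 1-month TBUT, so the imputation also matters for completeness.

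The cost is text edits to five sections, with no new data or visits, since both populations are already planned at 1 month. The estimate may be slightly less favourable, and OSDI power may fall if ITT dilutes the effect. At 90 per arm (SE = 18√(2/90) = 2.68) OSDI power is 88.3% undiluted, 84.9% with an assumed 5% dilution (8.08 points) and 80.9% with 10% (7.65 points). TBUT power with 10% dilution (1.8 s, fully correlated eyes) is 99.7%.

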12.3 SUBJECT ACCOUNTABILITY

A complete accounting of subjects by visit will be provided, including reasons for dropout, if known.

12.4 DEMOGRAPHICS AND BASELINE CHARACTERISTICS

Demographic variables gender, race, ethnicity, and age will be summarized for all enrolled subjects, along with medical history. Descriptive statistical summaries of pretreatment parameters (min, max, median, mean, standard deviation) will also be provided for each treatment arm. This includes baseline measurements for each of the study endpoints: TBUT, Meibomian Gland Secretion Score, Corneal Staining, Conjunctival Staining, OSDI Score, SANDE Score, and Eye Dryness Score.

All baseline measurements will be evaluated for adequate balance between the two treatment arms.

12.5 ENDPOINTS AND ANALYSIS METHODS

All primary and secondary endpoints will be evaluated at 1 month for submission for regulatory approval. Outcomes measured on a per-eye basis will be analyzed using linear mixed effect models to account for within-person correlation (correlation

CONFIDENTIAL Sight Sciences

between right and left eyes). If the primary endpoint is successful at 1 month, and for all successful secondary endpoints, treatment duration will be further evaluated at 3 and 6 months.

12.5.1 DESCRIPTIVE ANALYSES

All outcome measures, IOP outcomes, and Use of dry eye lubricants, will be tabulated by visit and treatment group.

12.5.2 PRIMARY EFFECTIVENESS ENDPOINT

The primary effectiveness outcome is the change from baseline in Tear Break-Up Time (TBUT) at the 1 month follow up. TBUT will be analyzed using a linear mixed effects (LME) model. This will allow for the proper incorporation of within-person correlation into the statistical model, and will also allow for adjustment for baseline measurements.

Details of the LME model are provided in the Statistical Analysis Plan (SAP) provided in Appendix C. Hypotheses regarding the primary and secondary effectiveness outcomes are described below in Section 12.6.

12.5.3 POOLABILITY

Using the LME modeling approach outlined above, poolability will be evaluated across centers by testing a Treatment-by-Center interaction (TxC). If the TxC interaction is significant at α =0.15 a Center effect will be included in the final model and results will be reported separately by Center. For this analysis, Centers with less than 5 enrolled subjects will be combined into a single virtual center.

12.5.4 MISSING DATA

[figure not shown]
As a sensitivity analysis, multiple imputations for the primary outcome at the 1 month time point will be carried out using baseline characteristics and 1-week outcomes as predictors. Details are provided in the SAP (Appendix C).

12.5.5 SECONDARY EFFECTIVENESS ENDPOINTS

The secondary effectiveness endpoints include change from baseline for the following outcomes:

- Ocular Surface Disease Index (OSDI) score,
- Total Meibomian Gland Secretion Score,
- 3. Corneal staining score,
- 4. Conjunctival staining score,

- 5. Symptom Assessment iN Dry Eye (SANDE) Frequency score, Severity Score and Total score.
- 6. Eye Dryness Score (EDS)

12.5.6 EVALUATION OF TREATMENT DURATION

If the primary endpoint is successful at the one month primary time point, then treatment duration will be evaluated using a hierarchical testing procedure. Using data that are obtained at the 3- and 6-month follow-up visits we will again test the primary hypothesis comparing change from baseline Tear Break-Up Time (TBUT) between the treatment and control. We will use the same linear mixed effects (LME) model as in the primary analysis, evaluating each time point separately. The two time points will be tested sequentially, stopping at 3 months if the test fails at that point. Treatment duration will be the maximum time point at which this treatment duration testing succeeds, either 1, 3, or 6 months.

This analysis will not be carried out if the primary 1-month endpoint fails, it is not intended to establish primary effectiveness in the event of study failure at one month.

Note that this analysis will be carried out using data that will be at least partially obtained after the primary database lock. However every effort will be made to maintain the masking of assessors through the 6-month follow-up as described in section 9.7.

This analysis does not affect the type I error for the primary endpoint. The 1- 3- and 6-month TBUT outcomes will likely be highly correlated, however the sequential testing will appropriately control the time-wise type I error rate.

For each secondary endpoint that is successful at the one month time point using the hierarchical testing procedure described in 12.5.5, treatment duration will be evaluated at the 3- and 6-month follow up. Evaluation of treatment duration for the secondary endpoints will be based on sequential testing of 3- and 6-month follow up times separately, in the same manner as for the primary endpoint. Secondary endpoints that fail at the 1-month time point will not be evaluated for treatment duration.

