23.1.5 EVALUATION OF TREATMENT DURATION

If the primary endpoint is successful at the one month primary time point, then treatment duration will be evaluated via comparisons of treatment versus control change in TBUT at each of the 3- and 6-month time points separately as described in 12.5.6.

For each secondary endpoint that is successful at the one month time point using the hierarchical testing procedure described in 12.5.5, treatment duration will be evaluated at the 3- and 6-month follow up. Evaluation of treatment duration for the secondary endpoints will be based on sequential testing of 3- and 6-month follow up times separately, in the same manner as for the primary endpoint. Secondary endpoints that fail at the 1-month time point will not be evaluated for treatment duration

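### The 3- and 6-month duration tests are sequential within each endpoint, but no visible rule controls false duration claims across the secondary endpoints

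*Combined protocol and SAP*

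**What the plan says.** Section 6.1 lists treatment duration endpoints, at 3 and 6 months, for whichever primary and secondary endpoints succeed. They stand apart from the exploratory endpoints.

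Section 12.5.6 gives the procedure.

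- **TBUT.** Duration is tested only after success at 1 month: "This analysis will not be carried out if the primary 1-month endpoint fails". Then "The two time points will be tested sequentially, stopping at 3 months if the test fails at that point". The latest visit that passes (1, 3 or 6 months) is declared the treatment duration.
- **Secondaries.** Entry is defined as "For each secondary endpoint that is successful at the one month time point using the hierarchical testing procedure described in 12.5.5". The method is the one used for TBUT: "Evaluation of treatment duration for the secondary endpoints will be based on sequential testing of 3- and 6-month follow up times separately". Section 23.1.5 repeats this and adds "Secondary endpoints that fail at the 1-month time point will not be evaluated for treatment duration".
- **Error control.** The section says that the duration analysis leaves the primary type I error untouched, and that "the sequential testing will appropriately control the time-wise type I error rate".

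Section 12.5.5 lists six secondaries. One of them is "Symptom Assessment iN Dry Eye (SANDE) Frequency score, Severity Score and Total score", so the count of secondary tests is 6 or 8. The public text does not show the details of the 1-month hierarchy, the content of Section 12.6 (hypotheses), or any alpha or sidedness for the duration tests.

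**The concern.** A fixed sequence lets every test run at full alpha because there is one chain and testing stops at its first failure. The duration rule, as far as it can be read, has several chains. Success on TBUT at 1 month opens the TBUT duration chain. Each secondary that succeeds at 1 month opens another. OSDI could be declared durable to 6 months after TBUT had failed at 3 months, and the same holds for each other secondary.

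The plan's assurance is about time, and it is correct for one endpoint. It says nothing about picking the endpoint that lasts longest. Section 4.2 seeks an indication covering signs and symptoms. TBUT is a sign, so any statement about how long symptom relief lasts would come from OSDI, SANDE or the Eye Dryness Score, which are the tracks without visible cross-endpoint control.

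**Working it through.** **1. The plan's own assurance.** The documents give no error rate for the duration tests, only the statement about control over time. A simulation of the 3-then-6-month sequence for one endpoint (400,000 draws, correlation 0.7 between visits, critical value 1.96) gives 2.5% false claims in one direction. This holds when no effect remains at either visit, and also when the effect is present at 3 months and gone at 6. The statement is correct, and the second time point adds no inflation.

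**2. Inputs for the check across endpoints.**

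- Tracks: TBUT plus 6 secondaries = 7, or TBUT plus 8 = 9 if the three SANDE scores count separately (Section 12.5.5).
- Level per track: two-sided 0.05, so 0.025 in favour of TearCare. This is an assumption.
- Correlation between endpoints: not given. Assumed equal for all pairs and varied from 0 to 0.7.
- Scenario: every counted endpoint succeeds at 1 month and none has an effect left at 3 months. A false claim on a track then requires a false rejection at 3 months, so each track contributes its nominal level once.

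**3. Formula.** With k independent tracks at level a, the chance of at least one false rejection is 1 − (1 − a)^k. With common correlation r, it is one minus the probability that k equicorrelated standard normal statistics all stay inside the critical limits, found by numerical integration.

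- k = 7, favouring TearCare: 1 − 0.975^7 = 16.2%
- k = 7, either direction: 1 − 0.95^7 = 30.2%
- k = 2, favouring TearCare: 1 − 0.975^2 = 4.9%
- k = 2, either direction: 1 − 0.95^2 = 9.75%

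| Tracks | Correlation | Favouring TearCare | Either direction |
|---|---|---|---|
| 7 | 0 | 16.2% | 30.2% |
| 7 | 0.3 | 13.7% | 27.1% |
| 7 | 0.5 | 11.5% | 23.0% |
| 7 | 0.7 | 8.9% | 17.8% |
| 9 | 0 | 20.4% | 37.0% |
| 9 | 0.7 | 10.1% | 20.2% |
| 2 (TBUT, OSDI) | 0 | 4.9% | 9.75% |
| 2 (TBUT, OSDI) | 0.7 | 4.2% | 8.4% |

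The reference values for a single endpoint are 2.5% and 5%. If all effects persist to 3 months and are gone at 6, the result is the same: simulation gives 16.4% for 7 independent tracks favouring TearCare.

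**4. How many tracks are likely to open.** Section 23.2.4 claims more than 90% power for TBUT and OSDI. For OSDI (difference 18.5 − 10 = 8.5, SD 18, two-sided 0.05), the normal approximation Φ(8.5 / (18·√(2/n)) − 1.96) gives 91.6% with 100 per arm and 88.6% with 90 completers per arm. At least two tracks is therefore the planned case. No power is stated for the other secondaries.

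**5. A repair that does not work.** One might carry the 1-month order forward visit by visit: all endpoints at 3 months in order, then those that passed at 6 months. Once TBUT passes at 3 months, this opens two tests at full alpha: TBUT at 6 months and the first secondary at 3 months. If both nulls are true and the tests are independent, the error is 1 − 0.95² = 9.75%, or about 9.8%. Control at 5% needs a single unbranched chain.

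**The case against.** The strongest reply is that the consequence is limited. The regulatory submission rests on the 1-month analysis (Section 12.8), the proposed indication contains no duration wording (Section 4.2), and Section 12.5.8 says that duration is judged primarily through TBUT. TBUT duration is one gated track held at its nominal level. The plan claims control over time only, and that claim is true. The pilot in Section 5.2.2 also reported results maintained to 6 months, so a complete loss of effect by 3 months is not what the documents lead one to expect. All of this stands and keeps the point moderate. It does not answer the gap, because Section 6.1 gives duration a formal tier for secondaries and Section 12.5.6 applies the TBUT procedure to each of them.

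A reader might also infer more than the documents support:

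- **That the 3- and 6-month tests run in parallel.** They do not. Only the endpoints run side by side.
- **That the plan assigns full alpha to every track, or discards its hierarchy after 1 month.** Neither can be stated as fact. The parts of Sections 12.5.5 and 12.6 where alpha, order or a cross-endpoint rule would sit are not in the public text. What can be said is that the duration text in Sections 12.5.6 and 23.1.5 uses the hierarchy only to decide 1-month success.
- **That the risk is 37%.** That figure needs nine independent tracks and counts rejections favouring warm compress. SANDE Total is computed from Frequency and Severity (Section 21.10.3), so nine independent tracks is not realistic.
- **That the primary result is compromised.** It is not. If nothing works at 1 month, the primary gate holds any duration claim at or below alpha.

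**Conclusion.** The point holds for the secondary duration claims. On the visible rule, error is controlled over time within each endpoint and is not controlled across endpoints. The relevant size is about 9% to 16% for at least one false claim favouring TearCare with 7 tracks, against 2.5%, and about 4% to 5% if only TBUT and OSDI open. Counting both directions with 7 tracks, it is 18% to 30% against 5%.

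These figures rest on an assumed two-sided 0.05 per track, on every counted endpoint succeeding at 1 month, on no effect remaining at the same later visit, and on correlations between 0.7 and 0. They are a conditional worst case, not an expected error rate. The 1-month primary analysis and the TBUT duration test are unaffected. The wording should be changed before the 3-month data are analysed.

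**What to change.** Add to Sections 12.5.6 and 23.1.5 that formal treatment-duration claims rest on TBUT, and that the 3- and 6-month p-values for secondary endpoints are nominal and support no formal duration claim. All planned analyses are kept.

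If formal secondary duration claims are wanted, specify one unbranched chain, with each test at full alpha:

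1. TBUT at 3 months
2. TBUT at 6 months
3. Each secondary in the 1-month order, 3 months and then 6 months

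Stop at the first failure, and treat a secondary that did not succeed at 1 month as a failure. This controls error over the set of duration claims. The 1-month secondary hierarchy remains a separate family, and the text should say so. State the alpha and sidedness of the chain in the same place.

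The cost is SAP wording only. The downside of the chain is that a secondary can lose its formal duration claim, including at 3 months, when TBUT fails at either visit or a higher-ranked secondary fails.
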